#### 4.3 Missing Data Considerations for Efficacy Analyses

If there is <5% of subjects with covariate data points missing, then no additional sensitivity analyses will be performed. If there are >=5% of subjects with missing covariate data, we will perform multiple imputation (MI). We will use the full conditional specification method (FCS) to impute missing data. If data have a monotone missing pattern, we will use linear regression to impute continuous variables, logistic regression to impute binary/ordinal variables, and the discriminant function to impute nominal variables. We will check normality of continuous variables. If very asymmetric, variables will be transformed. We will create 20 imputed datasets including all variables intended to be used in subsequent statistical analysis as a minimum. We will analyze the complete datasets using standard statistical analyses. Finally, the results from each model will be combined to produce inferential results.

If there is <5% of subjects with efficacy outcome data points missing, this will be considered a negligible amount and no additional sensitivity analyses will be performed. If there are >=5% of subjects with missing outcome data, the Mixed-Effect Model Repeated Measure (MMRM) approach is able to handle moderate amounts of missing data provided they are missing at random. However, it is difficult to rule out the possibility that at least some of the missing data are missing not at random (MNAR). We will apply a pattern-mixture approach to investigate the MNAR pattern. Specifically, we will define the missed visit indicator (1 if missing and 0 if observed). We fit a pattern-mixture MMRM model with this defined missed visit indicator. The coefficient of the missed visit indicator (e.g., gamma) is estimated and tested for statistical significance. If this coefficient is not statistically different from zero, missing at random assumption is valid. Otherwise, the missing is not at random. If the latter, we conduct an extensive sensitivity analysis by pre-specifying the value of gamma, which plays the role of sensitivity parameter to the MAR assumption. We define a grid in a plausible range of sensitivity parameter. For each pre-specified value, we investigate the treatment effect. When the pre-specified value is zero, the analysis assumes MAR.

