## Clarifications to Final SAP reflecting Primary Paper in the New England Journal of Medicine 05-15-2021:

- 1. Throughout the protocol and SAP, we refer to the ABC-SW, which is a modified subscale of the ABC-Lethargy, Social Withdrawal Subscale that eliminated questions 3, 32, and 53, which refer to lack of movement, in order to increase specificity for social reciprocity behaviors. In writing the primary paper, we wanted to eliminate any possible confusion with the original published ABC-Lethargy, Social Withdrawal subscale and referred to the modified scale as the ABC-modified Social Withdrawal subscale or ABC-mSW. We have changed our clinicaltrials.gov primary results to use the new nomenclature of ABC-mSW.
- 2. Reviewers pointed out that it was not entirely clear what our three secondary outcomes were. Therefore, we want to be clear that they are:
  - a. the Sociability Factor (abbreviated SF) which combines the ABC-mSW and the PDD-BI screening version in order to assess both areas of social reciprocity challenges and social skills (there was an error in the original version of the final SAP in which the sociability factor was inadvertently omitted from section 4.1.2, which has been corrected)
  - b.the Social Responsiveness Scale, 2nd Edition Social Motivation Subscale (abbreviated SRS-2-SM); c. the Stanford Binet, 5th edition Abbreviated Intelligence Quotient (abbreviated ABIQ).
- 3. Reviewers requested that we clarify what our sensitivity analyses were. They follow
  - a. Analysis using the original ABC-Lethargy, Social Withdrawal Subscale
  - b. Analysis integrating baseline (or screen if no baseline was available) plasma oxytocin level, baseline oxytocin level x treatment, and baseline oxytocin x treatment x time into the MMRM model
  - c. Analysis separately of the ABC-mSW outcome in the minimally verbal and fluently verbal subgroups.
  - d. Analysis of the ABC-mSW outcome in the per proctocol population
- 4. In the primary paper we also clarify that the full analysis set is essentially a modified intent treat sample, and that age group was dropped from the final analysis model because it was not significant.

Initial Statistical Analysis Plan for SOARS-B

Version 1.0

March 21, 2013

Study of Oxytocin in ASD to Improve Reciprocal Social Behaviors (SOARS-B)

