#### 2.1.3. Per-Protocol Population

The per-protocol (PP) population is defined as a subset of FAS who complete the full 24 weeks of double blind treatment with study drug (including those who stayed on the study drug for at least 22 weeks with 80% treatment compliance) and all assessments of the ABC-SW at baseline, Weeks 4, 8, 12, 16, 20 and 24. The per-protocol population will be used only for supportive analyses of the primary efficacy endpoint.

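### SAP v2.0 section 4.3 lets a significance test on gamma declare missing at random valid and decide whether the MNAR grid is run; observed data cannot settle either question

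*Combined protocol and SAP*

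**What the plan says.** SAP v2.0 section 4.3 handles missing outcomes in steps.

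- **Threshold.** "If there is <5% of subjects with efficacy outcome data points missing", the amount is called negligible and no sensitivity analysis follows. At 5% or more, the section relies on the mixed model, which it says is adequate if data are missing at random (MAR).
- **Caveat.** It concedes that "it is difficult to rule out the possibility that at least some of the missing data are missing not at random (MNAR".
- **Indicator.** For a pattern-mixture model, "we will define the missed visit indicator (1 if missing and 0 if observed". The level (per child or per visit) is not stated.
- **Decision.** Gamma, the indicator's coefficient, is estimated and tested. "If this coefficient is not statistically different from zero, missing at random assumption is valid"; otherwise the data are declared not missing at random.
- **Grid.** "If the latter, we conduct an extensive sensitivity analysis by pre-specifying the value of gamma". The section adds "We define a grid in a plausible range of sensitivity parameter" but gives neither limits nor direction, and it calls gamma a sensitivity parameter.

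The primary test is the treatment effect on the ABC-SW at week 24 (section 4.4). It comes from a model with week as a continuous variable and a random intercept and slope (section 4.2).

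**The concern.** One p-value decides two things: what the report may say about MAR, and whether the MNAR grid is produced. The week-24 comparison rests on MAR, and the grid is the only planned analysis that would show how far the result depends on it. A sensitivity parameter is varied because the data cannot fix its value. Letting its estimate decide whether to vary it contradicts that, and contradicts the section's own caveat that MNAR is hard to exclude.

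If gamma is not significant, a reader of the report would be told that MAR is valid and would see no departure from it.

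**Working it through.** The rule states no error rate or power, so there is no figure of the plan's to reproduce. The check is of logic first and size second.

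**1. Can the test separate MAR from MNAR?** It uses observed scores and the pattern of missed visits.

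- Add any constant to the unseen scores: every observed score and every indicator stays the same, so gamma and its p-value stay the same.
- Read per visit, the indicator is 0 on every row that has an outcome, so gamma cannot be estimated from those rows.
- Read per child, gamma compares observed scores of children with and without a missed visit. Under MAR those may differ, because MAR allows dropout to depend on earlier observed scores. Illustration under assumptions (290 children, six visits, week-24 SD 9, child-level flag, 600 simulated trials, log-odds of dropout rising 0.15 per point of the last observed score, 8.6% dropout): gamma was significant in 98.2% of trials, although the week-24 estimate averaged -0.02 against a true value of 0. In a separate simulation with 10% dropout and log-odds of 0.2, 0.5 and 1.0 per SD, the rates were 12, 46 and 96%. The rate depends on the assumed strength of the link.

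**2. Is non-significance evidence that gamma is zero?** The threshold is reached at 0.05 × 290 = 14.5, so 15 children. With 15 incomplete and 275 complete children, the SE of a single-visit difference is SD × sqrt(1/15 + 1/275) = 0.265 × SD. The SAP's SD range of about 5 to 9 (section 6) gives 1.33 to 2.39, and a 95% half-width (× 1.96) of 2.6 to 4.7 points. Using several visits would narrow this somewhat, but the upper end is close to the 5 points that section 6 calls clinically meaningful.

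**3. Does another part of the plan supply an unconditional MNAR analysis?**

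- The per-protocol set (section 2.1.3) requires "all assessments of the ABC-SW at baseline, Weeks 4, 8, 12, 16, 20 and 24", so it leaves out children who missed a visit.
- Protocol v6.0 section 10.1 compares observed data of dropouts and completers, and acts only if MAR looks untenable.
- Early-termination questionnaires (protocol v6.0 section 6.5) are completed near the last dose, which need not be week 24.
- The 2021 clarifications, under "Reviewers requested that we clarify what our sensitivity analyses were", list four analyses, none for missing data.

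None does.

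**4. How large could the effect be?** Inputs: visits at weeks 4, 8, 12, 16, 20 and 24; SD 9 and a 5-point shift (the SAP's planning difference, borrowed here as an assumed shift); 145 per arm. The share missing is assumed, because the only attrition figure (1%, section 6) replaces an allowance that ran from randomization to the first post-randomization visit.

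With week linear and the unseen scores filled in, the week-24 effect is a point on a fitted line. Number the visits x = 1 to 6. The weight of visit x is 1/6 + (6 − 3.5)(x − 3.5)/17.5, giving −0.19, −0.05, 0.10, 0.24, 0.38 and 0.52.

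Bias = shift × share missing in the shifted arm × sum of the weights of the shifted visits. That sum is 0.524 if only week 24 is shifted and 1.238 if weeks 12 to 24 are.

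| Assumed share missing, one arm | Week 24 only | Weeks 12–24 |
|---|---|---|
| 5% | 0.13 | 0.31 |
| 10% | 0.26 | 0.62 |
| 15% | 0.39 | 0.93 |

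For example, 5 × 0.10 × 0.524 = 0.26 and 5 × 0.10 × 1.238 = 0.62. As a rough yardstick, the two-group SE is 9 × sqrt(2/145) = 1.057, which ignores the missing data; 0.26 and 0.62 are then about 0.25 and 0.59 SE. If week were categorical, as in protocol v6.0 section 10.1, the figure at 10% would be 5 × 0.10 = 0.50, inside the same range.

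**The case against.** The case for leaving the rule alone has several parts.

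- **The effect is small and the threshold may never be reached.** The table supports modest size, and no document shows that 5% will be reached. But the threshold counts children with missing outcome data points: if a single missed visit counts, then with six visits and independent misses (an assumption) a miss rate of 1 − 0.95^(1/6) = 0.85% per visit is enough. A plan should be right for the case it provides for.
- **A significant gamma under true MAR does little damage.** This stands. The grid is then run, which is what is wanted, and the harm is a wrong label. The real harm is on the non-significant side.
- **The test may pick up some MNAR processes.** It can, when they leave a trace in earlier observed scores. Dropout that is MAR and driven by those scores leaves the same trace, so the test still does not discriminate.
- **Simulating unseen shifts adds nothing.** Correct. If only unseen values are changed after random dropout, rejection stays near 5% by construction. That restates the argument, so the conclusion here does not rest on it.

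A reader might infer from the 2021 clarifications that the test was used to suppress the grid. The documents do not support that: silence there is equally consistent with fewer than 5% of subjects having missing outcomes. A reader might also take the two-sided testing rule in section 2.2 as fixing the direction of the grid. It concerns tests and confidence intervals only.

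**Conclusion.** Wrong as written. A test on observed data cannot show that MAR is valid, and it should not decide whether the planned MNAR grid is reported. This rests on identifiability, not on any simulated rate.

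The primary model, the week-24 test and its alpha are unaffected. The likely size is modest: roughly 0.26 to 0.62 points for a 5-point shift in one arm with 10% missing there, both assumed. It would matter mainly for a result close to the significance boundary, in either direction.

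Two stronger readings are tempting. One is that the rule invalidates the primary result; nothing in the documents supports that. The other is that an exact shift can be named at which the conclusion would change. It cannot: the week-24 missingness is not given, the SE depends on it, and the bias per point of shift varies more than twofold (0.524 to 1.238 times the share missing) with the visits assumed to be shifted.

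**What to change.** In section 4.3, delete the significance test on gamma, the two sentences that declare the data missing at random or not, and the words that make the grid depend on the outcome. Replace them with:

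> Gamma is a sensitivity parameter and is not tested. Whenever 5% or more of subjects have missing outcome data for an efficacy variable, the grid analysis is run and reported for that variable, in the first place for the week-24 treatment effect on the ABC-SW, whatever the observed data show. Gamma is the assumed shift applied to unobserved values at every missed visit, may differ by arm, and covers both directions. The plausible range and step are fixed before unblinding. The treatment effect and its confidence interval are reported for each pair of arm-specific values, and the pairs at which the conclusion changes are identified, or it is stated that there are none.

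The text keeps the step for all efficacy variables, as section 4.3 does now. That matters for the abbreviated IQ, because the early-termination visit does not include IQ testing.

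The cost is modest extra programming and reporting. The programming specification must also say how unseen outcomes are predicted before the shift is applied, since the section's multiple-imputation text is for covariates. The data collected, the 5% threshold and the primary analysis do not change.

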### 4.4 Primary Efficacy Analysis

The primary efficacy response variable will be tested at the level of  $\alpha$  = 0.05. Longitudinal models as described in General Modeling Considerations will be fit with dependent variable of change from baseline to each post-baseline timepoint (weeks) up to week 24. The primary hypothesis test of interest will be a test of treatment effect at week 24.

As a sensitivity analysis, the primary efficacy analysis will also be conducted in the per-protocol population.

#### 4.5 Subgroup Analysis for Primary Efficacy Variable

As a secondary analysis for the primary efficacy variable, the interaction of treatment-by-functionality-by-week will be examined. In addition, the primary efficacy variable will be analyzed within the low and high functioning stratum separately.

### 4.6 Addition of Covariates to Primary Efficacy Analysis Model

As additional secondary analyses for the primary efficacy variable, the following groups of covariates will be added separately to the model in the primary efficacy analysis and tested for their significance:

Baseline age, treatment-by-age interaction, treatment-by-age-by-week interaction.

Baseline serum oxytocin, treatment-by-oxytocin interaction, treatment-by-oxytocin-by-week interaction.

In both cases, the primary test will be the significance of treatment-by-variable-by-week interaction, and if not significant, the treatment-by-variable interaction.

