### 2.2 General Summarization of Study Data

Unless otherwise specified, continuous variables will be summarized with descriptive statistics including n, mean, standard deviation (SD), median, first quartile (Q1) and third quartile (Q3) and minimum and maximum values. Categorical variables will be reported as number and percentage of participants in each category. Least squares (LS) means, standard errors, estimates of contrasts with 95% confidence intervals (CI), and p-values will be reported as appropriate.

All other statistical tests and confidence intervals will be 2-sided, unadjusted for multiplicity, and tested at  $\alpha$  = 0.05, except those explicitly stated to be otherwise.

All analyses and summaries will be produced using SAS® version 9.3 (or higher).

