#### 4.2 General Modelling Considerations for Efficacy Analyses

Unless otherwise specified, the primary model is mixed model with repeated measures (MMRM), with change from baseline to each post-baseline timepoint for a response variable, functioning (low versus high) as the stratification variable, center as a blocking factor, treatment (oxytocin versus placebo), week as a continuous variable, treatment and week interaction, and baseline value as a covariate, with random coefficients for the intercept and week, with an unstructured structure among the random coefficients. We will investigate the interaction of treatment, week, and functioning and adopt the most parsimonious model as the final model. Distributional assumptions will be examined using residuals. These mixed models could fail to converge or encounter difficulties based on their use of asymptotics. If they do, we will attempt to

simplify the models in order to eliminate the problems, and if necessary, move to analyses that assume compound symmetry, but use a Huynh-Feldt correction if compound symmetry fails.

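### The moderator models in SAP v2.0 section 4.6 omit variable-by-week, so the three-way test can read a time trend shared by both arms as effect modification

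*Combined protocol and SAP*

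**What the plan says.** Section 4.6 of SAP v2.0 adds two groups of terms, one at a time, to the primary model. For age they are "Baseline age, treatment-by-age interaction, treatment-by-age-by-week interaction". For oxytocin they are "Baseline serum oxytocin, treatment-by-oxytocin interaction, treatment-by-oxytocin-by-week interaction". The decision rule for both is that "the primary test will be the significance of treatment-by-variable-by-week interaction, and if not significant, the treatment-by-variable interaction".

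The model they join (section 4.2) has "week as a continuous variable, treatment and week interaction, and baseline value as a covariate, with random coefficients for the intercept and week". It supplies week and treatment-by-week, but no product of age or oxytocin with week. The first secondary objective (section 1.2.2) and the 2021 clarification of the oxytocin model name the same interactions and do not supply it either.

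On error rates, section 2.2 says "All other statistical tests and confidence intervals will be 2-sided, unadjusted for multiplicity, and tested at" α = 0.05. On timing, section 4.4 says "The primary hypothesis test of interest will be a test of treatment effect at week 24". Section 4.6 names no time point. SAP v2.0 does not give the coding of treatment, the centring of week, or whether the three-way term leaves the model before the second test.

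**The concern.** A three-way interaction tests effect modification only if all its lower-order terms are in the model. Here one is missing, and the three-way term takes over its work. If older and younger children simply improve at different rates, equally in both arms, the designated test can come out significant and be reported as a moderator of oxytocin's effect.

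Such a shared trend is plausible. Protocol v6.0 section 4.3 expects very young children to improve more, partly because they receive more intervention services, which has nothing to do with the assigned arm.

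Two further weaknesses are independent of the missing term. The fallback gives each moderator a second chance at 0.05, and it is not tied to week 24, where the primary hypothesis lies.

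Efficacy as a function of oxytocin level, age and functional level is the first-listed secondary objective. Section 2.3 has these models run before the secondary endpoints, and protocol section 2 expects the moderator analysis to support personalised treatment.

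**Working it through.** **Inputs from the documents.** N = 290, 1:1 allocation; post-baseline ABC-SW at weeks 4, 8, 12, 16, 20 and 24; SD of change 9. Section 4.6 gives no figure of its own. As a check on the sample-size section, a difference of 5, SD 9, two-sided 0.05 and 90% power give n = 2 × (1.960 + 1.282)² × 81/25 = 68.1, so 69 per arm per stratum (70 by exact t-test) against 71 stated. The plan's figure is reproduced closely.

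**Assumptions.** The documents give no slope variance. Three sets of intercept SD, weekly slope SD and residual SD were used, each with a week-24 SD of about 9. The moderator is continuous and standardised, there are no missing data, the covariance is treated as known, and baseline, functioning and center are left out. The shared trend is d points per SD of the moderator by week 24, identical in both arms.

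**What the three-way term tests.** Let λP and λO be the moderator-by-week slopes in the placebo and oxytocin arms. Effect modification over time means λO − λP ≠ 0.
- CLASS coding without variable-by-week: two columns, one slope per arm. The test is λP = λO = 0 on 2 df, and a common slope violates it.
- 0/1 coding: one column, non-zero only in the oxytocin arm. The placebo slope is forced to zero and the coefficient estimates λO alone.
- ±0.5 coding: the column is nearly orthogonal to a common trend.
- Age as three groups: under CLASS coding the term has 4 df without age-group-by-week and 2 df with it, so the fault is the same.

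**Size.** The weeks have mean 14 and sum of squares 280, so a child's fitted slope has variance v = (slope SD)² + (residual SD)²/280. The noncentrality is 290 × (d/24)²/v on 2 df for CLASS, and 145 × (d/24)²/v on 1 df for 0/1. For set A, v = 0.040 + 32.49/280 = 0.156, and at d = 1 the CLASS noncentrality is 290 × 0.001736/0.156 = 3.23.

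| Set (SDs) | v | CLASS, d = 1 / 2 | 0/1, d = 1 / 2 |
|---|---|---|---|
| A (5, 0.20, 5.7) | 0.156 | 34% / 91% | 25% / 72% |
| B (3, 0.28, 5.2) | 0.175 | 31% / 87% | 22% / 67% |
| C (6, 0.12, 6.0) | 0.143 | 37% / 93% | 26% / 76% |

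Simulation of the same sets (1,000 runs per cell) agrees: CLASS 30-38% at d = 1 and 88-92% at d = 2; 0/1 coding 22-25% and 68-73%; ±0.5 coding 5-8%. A second simulation with other assumed variances gave 37-96% (CLASS) and 26-82% (0/1) over the same trends. The upper ends correspond to v of about 0.123, since 290 × (2/24)²/0.123 = 16.4 gives 96% on 2 df, and half of that gives 82% on 1 df. With variable-by-week added, the three-way test returned to 4.3-5.9%.

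**Two-step rule, complete model, no modification.** Two independent tests give 1 − 0.95² = 9.75% per moderator; four tests over two moderators give 1 − 0.95⁴ = 18.5%. Simulated per-moderator rates (3,000 runs) were 8.3-8.7% with the three-way term kept and 9.3-10.0% with it dropped.

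**What the fallback estimates.** In the full model the interaction at week w is γ + wδ, with γ the two-way and δ the three-way coefficient. If the three-way term is kept and week is uncentred, γ is the interaction at week 0. If it is dropped, γ is a constant interaction over weeks 4-24. Suppose true modification grows linearly to 3 points per SD at week 24 (assumed):
- week-0 coefficient: 5% power;
- three-way term dropped: estimate 1.0-1.6 points, 41-52% power;
- contrast γ + 24δ: estimate 3.0 points, 86-89% power.

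**The case against.** Several stronger readings are tempting and the documents do not support them.

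- A reader might infer that the second test concerns week 0. That needs the three-way term kept and week uncentred, and v2.0 states neither. The parsimony rule in section 4.2, written for functioning, suggests dropping a non-significant term. With week categorical, as in protocol v6.0 section 10.1, the usual test would average over visits. What stands is that none of these is a week-24 test.
- A reader might infer that any prognostic variable will be declared a moderator. The variable's main effect is in the model, so a prognostic effect that is constant over weeks is absorbed. Only a trend that changes over weeks is misattributed.
- A reader might blame the two-step rule for the misattribution. The missing term causes it; the rule adds a separate and smaller inflation.
- CLASS coding appears only in the v1.0 sample code, and centred coding nearly removes the fault. That is true, but a test whose validity turns on an unstated coding choice is not adequately specified.
- The summary of SAP changes says age group was used rather than age in months, so the percentages for a continuous moderator do not carry over exactly to age. The mechanism does.
- If change starts at zero and modification is linear, 24 times the three-way slope is close to week-24 moderation, so the first test of a complete model addresses it in substance. What is missing is the formal contrast.
- Unadjusted testing is disclosed, and one test is named as primary. That makes the 8-10% a known cost, but the plan does not state it.

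**Conclusion.** The concern holds in this form. Followed as written with CLASS or 0/1 coding, the section 4.6 three-way test can declare effect modification where there is none: in about 30-96% and 22-82% of trials respectively, for a shared trend of 1 to 2 points per SD by week 24. Those ranges rest on the assumed trend and variances. The direction of the fault does not; it follows from the list of terms and the coding. With no shared trend, or with centred coding, the test is close to nominal.

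The two-step rule separately yields about 8-10% false declarations per moderator, and no week-24 moderation test is specified. A reader might also infer that the primary result is compromised. It is not: section 4.6 covers additional secondary analyses and leaves the type I error of the section 4.4 test unchanged. The treatment-by-functioning analysis in section 4.5 has no two-step rule and is outside this point.

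**What to change.** In section 4.6:

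1. Add variable-by-week to each covariate group: age-by-week (age-group-by-week if age group is used) and oxytocin-by-week.
2. State the treatment coding and the centring of week.
3. Replace the two-step rule with one prespecified test per moderator: the treatment-by-variable contrast at week 24 from the full model, that is, the two-way coefficient plus 24 times the three-way coefficient with week uncentred. For age group, use the joint contrast over groups.
4. Report the other interaction terms descriptively.

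The list in the 2021 clarification of the oxytocin model should be brought into line. The cost is SAP wording and one estimate or contrast statement per moderator, with no new data. In the simulation, the week-24 contrast from the full model rejected in 4-6% of trials without modification.
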